# STUDY PROTOCOL

## 1. Background

An aging population is a global phenomenon (1) and likewise, Singapore is experiencing a rapid increase in the mean population age as well (2). The process of aging results in a progressive decline of numerous physiological processes, leading to an increased risk of health complications and cardio-metabolic diseases (3). Since aging significantly affects the heart and arterial systems (4, 5), it has been associated with an increased risk of developing cardiovascular disease (CVD) (3).

CVD is one of the world's leading causes of death (6). In Singapore, 30 % of all total deaths or 16 deaths daily are attributed to CVD in 2016 (7). Many significant risk factors for CVD have been identified (8) and endothelial dysfunction due to oxidative stress and inflammation in the artery is considered as a major risk factor for CVD development (9–11). Mounting evidence emphasised the importance of measuring clinically relevant markers of the endothelial dysfunction when conducting CVD-related research beyond assessing the conventional blood lipid profiles.

Endothelial dysfunction-related clinical markers include endothelial progenitor cells (EPCs), brachial artery flow-mediated dilation (FMD) and carotid intima-media thickness (IMT).

Circulating EPCs are bone marrow-derived mononuclear cells that have the capacity to migrate, proliferate, and differentiate into mature endothelial cells (12). EPCs also play crucial roles in the regeneration of the endothelial lining of blood vessels (13). Clinical studies documented a decreased number of circulating EPCs in CVD patients, suggesting that levels of circulating EPCs might be associated with vascular endothelial function and CVD risk (14–16). Brachial artery FMD and carotid IMT are well-known markers of early atherosclerosis, which significantly correlates with the development of CVD (17–19). Hence, an assessment of the circulating EPC, coupled with brachial artery FMD and carotid IMT can serve as surrogate markers of vascular endothelial function and indicate subclinical vascular pathological changes (20, 21).

Furthermore, the global study of molecular lipids through the use of lipidomic technologies can provide a better understanding of the cardiovascular pathological states caused by alterations in lipid metabolism (22). Plasma lipid species and classes/subclasses have been found to be associated with CVD (23). More recently, plasma lipid species have also been associated with incidences of cardiovascular events, suggesting the usefulness of these biomarkers to predict

cardiovascular risk (24).

Nonetheless, there is a paucity of data from human clinical studies that observe the synergistic effects of wolfberry and healthy eating patterns on cardiovascular health. In addition, very limited studies apply novel analytical techniques to assess the complex cardiovascular pathological states in the nutrition field.

## 1.1 General introduction

The American Heart Association and other organizations recommended a healthy diet and lifestyle to combat CVD (25). Thus the development of a dietary strategy that improves endothelial function of the artery and regulates other CVD risk factors may reduce the risk of developing CVD. Although there is a growing of interest on evaluating both structural and functional arterial proprieties and assessing plasma lipidomic profiles when applying nutritional treatment, very limited data exist in the nutrition field.

The fruit of *Lycium barbarum*, also called wolfberry or goji berry, is a well-known traditional Chinese medicine plant and it has recently become increasingly popular in many countries around the world due to its health promoting properties (26, 27). The biological activities and potential health benefit effects of wolfberries are generally explained by its chemical constituents including carotenoids, polysaccharides, and polyphenols (28). Among the various carotenoids, zeaxanthin, which has antioxidant and anti-inflammatory properties is predominant in wolfberry (26). In humans, zeaxanthin is located primarily in the macula and is believed to protect the retina from photo-oxidative damage by its antioxidant function (28). In addition, cardio-protective effects of zeaxanthin has been discussed and epidemiologic studies have shown strong associations between carotenoids, including zeaxanthin, and the risk of CVD and atherosclerosis (29). Although the effects of wolfberry extract or wolfberry supplementation on blood carotenoid concentrations and blood lipid and antioxidant status have been reported (30–32), the cardio-protective effect of consuming dried wolfberry as a whole food is limited.

Healthy eating patterns such as the Mediterranean diet, has also been linked to a reduced risk of CVD. Several mechanisms have been suggested to underlie the observed benefits including a decrease in inflammatory markers, an improvement in endothelial function, and reduced LDL atherogenicity (33–35). Only one recent study investigated the plasma lipidomic profiles with the

Mediterranean diet and there was an alteration of lipid metabolites with a longer acyl chain and higher number of double bonds after the Mediterranean diet (35). The Health Promotion Board (HPB) in Singapore recommends a healthy eating pattern “My Healthy Plate”, to help Singaporeans practice healthy eating habits that can aid in weight control and chronic disease protection. To date, no study has assessed the impact of this healthy eating pattern against CVD risk in the Singapore population.

Thus collectively, consuming a wolfberry as part of a healthy eating pattern diet may improve endothelial function and alter lipid metabolites in Singapore’s middle-aged and older adults who are at risk for CVD.

## **1.2 Rationale and justification for the study**

CVD is a major disease burden which is constantly growing in Singapore. Moreover, with the rapid increase in the local older population, the cost and manpower for CVD care, particularly in older population, is becoming unsustainable. Due to this circumstance, it is very important to seek ways to resolve healthcare challenges by taking necessary preventative measures to improve CVD care

### **1.2.1 Rationale for the Study Purpose**

Findings from the proposed research will provide the scientific evidence regarding the beneficial effects of consuming wolfberry with a healthy eating pattern diet on the 1) cardiovascular system, 2) lipidomic profiles, and 3) whole body anti-oxidant status in Singapore middle-aged and older individuals. Although EPC, brachial artery FMD, and carotid IMT are the significant clinical markers of endothelial function and cardiovascular health, they are rarely measured in the nutrition field particularly in middle-aged and older population. Beyond the conventional blood lipid profiles, the importance of assessing the structure and function of the complete set of lipids is emerging, however, the application of lipidomic technologies is very limited in the nutrition-related research projects as well.

Therefore, the outcomes of this project will support/validate the assessment of clinically relevant cardiovascular health-related indicators and the complete set of lipid metabolites in this population when applying nutritional treatment. Lastly, the results from the proposed research will assist a practical guidance of dietary behaviour changes providing cardiovascular health

promoting effects to a large proportion of the Singapore population and may result in reducing cost and manpower for CVD care.

### **1.2.2 Rationale for Doses Selected**

Dose have been selected based on studies by Zanchet et al. 2017(14 g/day) (32) and Cheng et al. 2005 (15 g/day) (31) which likewise conducted clinical randomised controlled trials with whole dried wolfberry. Favourable outcomes on the cardiovascular health of the subjects post-intervention were observed with a similar dose of 15 g wolfberry/day.

### **1.2.3 Rationale for Study Population**

The age demographics of the selected population will include only the middle-aged and older adults between 50 to 75 years old. The rationale for this selection is because of their lower threshold and higher susceptibility toward CVD manifestation since the structural and functional deterioration of the heart and arterial systems is associated with aging (1).

### **1.2.4 Rationale for Study Design**

This is a 16-week parallel, single-blind (investigator), prospective randomised controlled trial (RCT). Specifically, the 16 week duration was selected to allow us to investigate the cardiovascular protective effects of our intervention diets.

## **2. Objectives and Hypothesis**

### **2.1 Objectives**

1. To assess the effects of consuming a wolfberry as part of a healthy eating pattern diet on endothelial function in middle-aged and older adults.
2. To assess the effects of consuming a wolfberry as part of a healthy eating pattern diet on lipidomic profiles in middle-aged and older adults.
3. To examine the effects of consuming a wolfberry as part of a healthy eating pattern diet on whole body carotenoids and anti-oxidant status in middle-aged and older adults.

### **2.2 Hypothesis**

1. Consuming wolfberry with a healthy eating pattern diet will improve endothelial function when compared to a same diet without wolfberry.

2. Consuming wolfberry with a healthy eating pattern diet will improve the whole body carotenoid and oxidative stress status of subjects compared to those who consumed a similar diet without wolfberry.
3. Consuming wolfberry with a healthy eating pattern diet will improve blood and skin carotenoids status while decrease whole body oxidative stress status when compared to a same diet with no wolfberry.

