2. Blood carotenoid concentration: Fasting state lutein, zeaxanthin, lycopene,  $\alpha$ -carotene,  $\beta$ -carotene,  $\alpha$ -cryptoxanthin, and  $\beta$ -cryptoxanthin concentrations using high-performance liquid chromatography (HPLC; pre- and post-intervention only).
3. Oxidative stress and inflammatory-related parameters: Concentrations of plasma oxidative stress (malondialdehyde (MDA), glutathione peroxidase (GPX), and superoxide dismutase (SOD)) and inflammatory (tumour necrosis factor- $\alpha$ , interleukin-6, monocyte chemoattractant protein-1) biomarkers using commercially available ELISA assay kits (pre- and post-intervention only).
4. Concentrations of vasodilation and vasoconstriction-related biomarkers: nitric oxide, endothelial nitric oxide synthase, and endothelin-1 using commercially available ELISA assay kits (pre- and post-intervention only).
5. Endothelial progenitor cells will be analyzed and enumerated using flow cytometry.
6. Lipidomic profiles: The main classes of glycerophospholipids (phosphatidylcholine, phosphatidylserine, phosphatidylglycerol, phosphatidylinositol, phosphatidylserine, including lysoglycerophospholipids) and sphingolipids (sphingomyelin and ceramides) will be analysed at pre- and post-intervention by high-performance liquid chromatography couple with targeted MRM analysis on triple-quadrupole mass spectrometers (pre- and post-intervention only).
7. Additional plasma will be stored for possible further analyses.

At the end of the subject's first visit, they will also be randomised into either the intervention or control arm using SAS 9.4 software although the intervention will only begin the following week.

One-to-one dietary counselling for each subject and an instruction sheet "My Healthy Plate dietary guide" will be provided by a research dietitian and trained research staff to achieve the healthy eating pattern diet while only subjects in the wolfberry intervention group will receive a provision of 500 g dried wolfberries every 4 weeks along with specific instructions to cook and consume 15 g/day wolfberry as part of a mixed-meal. Compliance with the diet interventions will be promoted by frequent online and in-person contact, 3-day food records (every 4 weeks) as well as photographs of the subject's meals which will be sent to the study personnel for regular checks on pre-determined dates.

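### Objective 2 (lipidomics) has no hypothesis, and the only rule for its panel of lipids is p<0.05 with no allowance for the number of tests

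*Combined protocol and SAP*

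**What the plan says.** Section 2.1 has three objectives. The first is endothelial function and the third is carotenoid and antioxidant status. The second reads "To assess the effects of consuming a wolfberry as part of a healthy eating pattern diet on lipidomic profiles", with no direction, lipid class or contrast.

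Section 2.2 has three hypotheses. Hypothesis 1 matches Objective 1: the diet with wolfberry "will improve endothelial function when compared to a same diet without wolfberry". Hypothesis 2 reads "Consuming wolfberry with a healthy eating pattern diet will improve the whole body carotenoid and oxidative stress status of subjects", against a similar diet without wolfberry. Hypothesis 3 says that the diet with wolfberry "will improve blood and skin carotenoids status while decrease whole body oxidative stress status". The second and third overlap in substance, and neither concerns lipids.

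Section 6.3.2 describes a targeted mass-spectrometry panel, measured before and after the intervention only. The glycerophospholipids are given as "phosphatidylcholine, phosphatidylserine, phosphatidylglycerol, phosphatidylinositol, phosphatidylserine, including lysoglycerophospholipids". The sphingolipids are sphingomyelin and ceramides. The number of individual species is not given.

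Section 11.2 tests the effects of meal, time and their interaction by repeated-measures ANOVA for all dependent variables and accepts significance at two-tailed p<0.05. It does not mention lipids, name a lipidomic endpoint or give a multiplicity rule. Section 11.1 names endothelial function as the primary outcome and bases the sample size on plasma zeaxanthin and malondialdehyde.

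**The concern.** A lipid panel yields many results per participant. Without a stated hypothesis, a named contrast or an error rate for the panel as a whole, any lipid below 0.05 can be offered as the answer to Objective 2. The plan does mean to make such a claim: section 1.2.1 expects the findings to be evidence of benefit on lipidomic profiles. Section 11.1 reserves the endothelial results for effect-size estimation, but nothing similar marks lipidomics as exploratory. The risk is that chance findings are published as effects of wolfberry and later studies are built on them.

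**Working it through.** The plan gives no lipidomic figure to reproduce, and the point does not depend on the sample size.

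**Step 1: match objectives to hypotheses.**

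| No. | Objective (2.1) | Hypothesis (2.2) |
|---|---|---|
| 1 | Endothelial function | Endothelial function |
| 2 | Lipidomic profiles | Carotenoids and oxidative stress |
| 3 | Carotenoids and antioxidant status | Carotenoids and oxidative stress |

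Three objectives face three hypotheses on two topics; none is on lipids. The nearest statement elsewhere, at the end of the general introduction (1.1), says only that lipid metabolites may change.

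**Step 2: count the named classes (6.3.2).** There are five glycerophospholipid entries, four of them distinct because phosphatidylserine appears twice, plus two sphingolipid classes. That makes 5 + 2 = 7 entries and 4 + 2 = 6 distinct classes, not counting lyso-forms separately.

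**Step 3: apply the rule in 11.2.** Take k lipid measures, one arm comparison each, α = 0.05, all nulls true and tests independent.

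- Chance of at least one false positive = 1 − (1 − 0.05)^k
- Expected number of false positives = 0.05 × k

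| k | Source of k | Chance of at least one | Expected number |
|---|---|---|---|
| 6 | distinct named classes | 1 − 0.95^6 = 0.265 | 0.3 |
| 7 | all entries, if each were a class | 1 − 0.95^7 = 0.302 | 0.35 |
| 20 | assumed species count | 1 − 0.95^20 = 0.642 | 1 |
| 100 | assumed species count | 1 − 0.95^100 = 0.994 | 5 |

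Correlation between lipids changes the chance, usually downwards, but not the expected number. Only one comparison per lipid is counted here. Section 11.2 also tests two main effects, so the count is conservative.

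**Step 4: which comparison answers Objective 2.** Both arms receive the dietary counselling (6.3.2), so a time effect can arise without wolfberry. The meal main effect averages values from before and after the intervention. With two time points, the arm-by-time interaction is the between-arm comparison of change, which is the contrast that isolates wolfberry.

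**Step 5: after adjustment.** When every null is true, the false discovery rate equals the chance of any false positive. Benjamini-Hochberg at 5% therefore holds that chance to at most 0.05 within the class totals and 0.05 within the species, under independence or positive dependence. Across both sets it is at most 0.05 + 0.05 = 0.10.

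**The case against.** The strongest reply is that section 11.2 speaks only of dependent variables and section 6.3.2 describes classes. Testing each species is an inference, and at class level the chance is about 26%, not near-certainty. That stands, and it is why the size must be given as a range. It does not remove the problem: no other rule covers the panel, and 26% is still about five times the nominal 5%.

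A second reply is that Objective 2 asks only for an assessment of effects, which estimated arm differences can provide, and that lipidomics is not the primary outcome. This also stands. A reader might infer that the trial cannot answer its second objective, but the documents do not support that. They show only that the plan does not say which lipid results would count as evidence.

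Three other stronger readings are tempting:

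- **A lost class.** The repeated phosphatidylserine entry might suggest that another class was intended and will go unmeasured. The text does not show this. The word may simply have been repeated, and the list summarises the main classes; it is not the assay's transition table. The entry also matters little to error rates (0.265 against 0.302).
- **Double counting.** Hypotheses 2 and 3 overlap, but no alpha is assigned by hypothesis, so the repeated wording creates no second test.
- **Overpromised scope.** Section 1.2.1 refers to "the complete set of lipid metabolites in this population", while the panel covers glycerophospholipids and sphingolipids. That sentence is rationale about supporting the assessment of these lipids, not a commitment in the analysis plan.

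**Conclusion.** The point holds as a multiplicity gap for a non-primary objective. If section 11.2 is followed as written, false positives in the lipid panel are not controlled. The size runs from about a one-in-four chance of at least one (six classes) to near-certainty (100 species). This rests on true nulls, independent tests, one comparison per lipid, and species counts that are assumed because the documents give none. The mismatch between 2.1 and 2.2 contributes because it leaves no stated lipid result to test; by itself it is a wording error, as is the repeated class name. The primary outcome and the sample size are not affected.

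**What to change.** In section 11.2, before any lipidomic results are seen:

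1. State that Objective 2 is judged on the arm-by-time comparison, that is, the between-arm difference in change.
2. Apply Benjamini-Hochberg at a 5% false discovery rate across the class totals and, as a second set, across the individual species. List the class totals and state the number of species. The class totals need the adjustment too: six tested without it still carry the 0.26.
3. Label unadjusted lipid p-values as exploratory.

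As minor wording corrections, align Hypothesis 2 with Objective 2, ask the laboratory to check the repeated phosphatidylserine entry in 6.3.2, and confine the lipid wording in 1.2.1 to the classes measured.

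No new samples or visits are needed. The cost is that fewer lipids will be called significant. Bonferroni gives a bound for the class totals, because Benjamini-Hochberg is never stricter. Take 20 per arm and a true difference of 1 SD, an assumed effect, so that 1/√(2/20) = 3.162. Power is Φ(3.162 − 1.960) = 0.885 unadjusted. At 0.05/6 it is Φ(3.162 − 2.638) = 0.700. The loss per class is therefore at most about 0.885 − 0.700 = 0.185 under these assumptions.

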## **2.3 Potential Risks and benefits**

### **2.3.1 End Points – Efficacy**

No benefit is guaranteed and you may not derive any benefit from participating. However, you will be able to contribute to knowledge with regards to the effects of a wolfberry enriched healthy diets on improvements in cardio-metabolic health in the middle-aged and older population.

### **2.3.2 End Points – Safety**

There may be potential risks to human participants but they are minimal and the research group members and well-trained technicians will consistently pay close attention to ensure the participant's safety. More details are described below.

1) Source of Materials: All data will be used solely for research purposes. The blood will be collected by an invasive procedure (intravenous cannulation) following a standard procedure provided by WHO (36) and collected blood samples will be used to measure selected clinical markers of health only. Other research materials will include: medical, diet logs, body composition, FMD and CIMT measurements. The original paper copies of all identifiable data will be kept in locked storage cabinets and rooms with access limited to [name], [name], [name] and her research staff. Electronic copies of the data with identifiable participant information will be kept on a secure website or password-protected computers with access limited to [name], [name], [name] and her research staff. All data will be de-identified prior to statistical analyses.

2) Blood Collections: Participants may experience soreness and bruising at the puncture site. Participants may also feel lightheaded and there is a slight risk of fainting. Direct pressure will be applied over the puncture site to minimize soreness and bruising. Participants will be seated in a cushioned chair with padded armrests to minimise the risk of falling if a participant becomes

lightheaded or faints during the blood draw. [name] trained research staff will stay with participants at NUHS IMU and NUS OHC during the blood collection to assure the participant's safety. Participants will be asked not to donate blood for at least one month prior to, during, and for one month after the study due to potential alterations in the participant's blood profile that may affect study outcomes. In the unlikely event that the subject is injured while giving a blood sample, first aid will be provided and the subject will be directed to proper health treatment by the on-site study physicians.

- 3) Dietary Intervention: There is no known risk associated with the consumption of wolfberry or a healthy eating pattern diet according to earlier intervention studies of a similar nature (30–32) but there is a possibility of the stomach or bowels becoming upset if there is a change in usual customary dietary intakes. Subjects who experience these symptoms will be closely monitored and instructed to modify their wolfberry intake pattern by distributing the intake of wolfberry over 3 meals instead. If the symptoms persist, the Principal Investigator and/or the Co-investigator of this study may stop the subject's participation at any time if it is decided that it is in his/her best interests. If significant new findings develop during the course of this research that may relate to the subject's willingness to continue participation, they will be provided with this information.
- 4) Resonance Raman Spectroscopy: There is no known risk associated with non-invasive resonance Raman spectroscopic analysis which involves only the exposure of the palm to visible blue light.
- 5) Dual-energy X-ray absorptiometry (DXA): Body composition will be measured through non-invasive procedures. Specifically, body density will be determined using DXA. DXA involves some exposure to radiation; however, it is very small. The average absorbed dose of radiation, per scan, is equal to 1.424 mRem, totaling 4.272 mRem for all 3 scans. This amount of radiation exposure is less than or equal to one percent of the average exposure from a chest x-ray (5-20 mRem), and less than or equal to one-tenth of one percent of the average exposure from a full dental x-ray series (50-300 mRem).
- 6) High frequency ultrasonographic imaging: Ultrasonographic imaging has been used for over 20 years with excellent record. It is based on non-ionizing radiation and is generally considered safe when used prudently by appropriately trained healthcare providers (37).

